1.2. Benefit/Risk Section

For the most recent information about the benefit/risk assessment of Ad26.ZEBOV and MVA-BN-Filo, refer to the latest versions of the Investigator's Brochures.^{5,6}

1.2.1. Known Benefits

The clinical benefit of prime-boost combinations of Ad26.ZEBOV and MVA-BN-Filo is to be established.

1.2.2. Potential Benefits

Subjects may benefit from clinical testing and physical examination in the Phase 1, 2 and 3 clinical studies and from continued contact for safety follow-up in the current study; others may benefit from the knowledge that they may aid in the development of an Ebola vaccine.

1.2.3. Known Risks

To date, there are only limited data from the Phase 1 studies with Ad26.ZEBOV and MVA-BN-Filo available. However, Ad26- and Ad35-based vaccines with other gene inserts have been administered to a limited number of human volunteers in clinical studies. These other vaccines mainly elicited some solicited local and systemic reactions, as expected with injectable vaccines, and no serious safety concerns in study participants. MVA-BN-based vaccines have been administered to more than 8,100 individuals without unexpected or serious adverse reactions reported. For details, see the safety data presented in Section 1.1.

1.2.4. Potential Risks

The following potential risks for Ad26.ZEBOV and MVA-BN-Filo will be considered in this study, taking into consideration that this rollover study does not include further administration of the candidate vaccines during the study period:

Vaccine Induced Seropositivity (VISP)

In general, uninfected subjects who participate in Ebola vaccine studies may develop Ebola-specific antibodies as a result of an immune response to the candidate Ebola vaccine, referred to as VISP. These antibodies may be detected in Ebola serologic tests, causing the test to appear positive even in the absence of actual Ebola infection. VISP may become evident during the study, or after the study has been completed.

Pregnancy and Birth Control

The effect of the study vaccines on a fetus or nursing baby is unknown, as well as the effect on semen. Therefore, a pregnancy with estimated conception within 28 days of vaccination with MVA-BN-Filo or within 3 months of vaccination with Ad26.ZEBOV in a female subject vaccinated with Ad26.ZEBOV and/or MVA-BN-Filo in Phase 1, 2 or 3 clinical studies will be followed up in this study. This study includes no further requirements for birth control as all rollover subjects have completed the vaccination phase.

There may be other serious risks that are not known.

1.2.5. Overall Benefit/Risk Assessment

Since this is an observational safety study, there is no additional risk by participating in this study.

1.3. Overall Rationale for the Study

The safety profile of Ad26.ZEBOV and MVA-BN-Filo needs to be established through evaluation of safety data for periods longer than those that are available from the Phase 1, 2 and 3 clinical studies. Extended follow-up permits the identification of serious adverse events not detected during initial follow-up period in the vaccine clinical study. A long-term observational study will permit the collection of product safety information over an extended period of time, without affecting the requirement for brief clinical studies to support a responsive cycle of clinical development decisions. Additionally, the establishment of a long-term safety study for follow-up of subjects exposed to Ad26.ZEBOV and/or MVA-BN-Filo has been requested by Health Authorities of countries where Phase 1, 2 or 3 clinical studies will be conducted.

2. OBJECTIVES AND HYPOTHESIS

2.1. Objectives

This study will document the long-term safety profile of Ad26.ZEBOV and MVA-BN-Filo in subjects previously exposed to these vaccines in a Phase 1, 2, or 3 clinical study and aims to address gaps in the currently available data for the risks of Ad26.ZEBOV and/or MVA-BN-Filo.

The study objectives are:

- To collect serious adverse event information from subjects exposed to Ad26.ZEBOV and/or MVA-BN-Filo in a Phase 1, 2, or 3 clinical study, for a total of 60 months after prime vaccination (including the duration in the subject's original study).
- To collect pregnancy outcomes (including spontaneous/elective abortion, intrauterine death/stillbirth, information on delivery) and serious adverse event information during pregnancy from female subjects who became pregnant with estimated conception within 28 days after vaccination with MVA-BN-Filo or within 3 months after vaccination with Ad26.ZEBOV in a Phase 1, 2 or 3 clinical study.
- To collect serious adverse event information for up to 60 months after birth from children born to female subjects who became pregnant with estimated conception within 28 days after vaccination with MVA-BN-Filo or within 3 months after vaccination with Ad26.ZEBOV in a Phase 1, 2 or 3 clinical study.

2.2. Hypothesis

This is a descriptive study to document the long-term safety profile of Ad26.ZEBOV and/or MVA-BN-Filo and to address gaps in the currently available data for the risks of Ad26.ZEBOV and/or MVA-BN-Filo. As this study aims to describe the data for benefit-risk assessment purposes, no hypotheses are pre-specified.

3. STUDY DESIGN AND RATIONALE

3.1. Overview of Study Design

This is a multi-country, prospective, long-term clinical safety study designed to extend the total follow-up period of vaccinated subjects up to 60 months (including the duration in the subject's original study), to allow collection of serious adverse events and pregnancy outcomes (including

spontaneous/elective abortion, intrauterine death/stillbirth, information on delivery) following administration of Ad26.ZEBOV and/or MVA-BN-Filo for the prevention of Ebola virus disease among subjects who participated in a Phase 1, 2 or 3 clinical study. In addition, offspring from vaccinated female subjects who became pregnant with estimated conception within 28 days after vaccination with MVA-BN-Filo or within 3 months after vaccination with Ad26.ZEBOV in a Phase 1, 2 or 3 clinical study will be followed up to 60 months after birth. Up to approximately 3,000 subjects may potentially be enrolled in this study, based on the number of exposed subjects in the contributing Phase 1, 2 or 3 clinical studies.

Since validated assays are not available yet to assess immune responses in the ongoing Phase 2 and 3 studies, unblinding of these studies has been delayed. Therefore, subjects in the ongoing Phase 2 and 3 studies who reach the last study visit will be approached to consent for enrollment into the VAC52150 Vaccine Development Roll-over study for long-term safety surveillance (for a total of up to 60 months after the prime vaccination). After unblinding of their original study only subjects who received Ad26.ZEBOV and/or MVA-BN-Filo will remain in this VAC52150 Vaccine Development Roll-over study for long-term safety surveillance. After unblinding, subjects who received placebo and have already been enrolled into the VAC52150 Vaccine Development Roll-over study will be discontinued from further participation in this roll-over study. This also applies to pregnant subjects who received placebo (ie, subjects enrolled in Cohort 2) or offspring from vaccinated female subjects who received placebo (ie, subjects enrolled in Cohort 3).

The study will consist of an enrollment visit, a number of follow-up contacts and an end-of-study contact. These contacts are preferably conducted by phone; if not possible, a study site visit needs to be organized. Preferably, offspring from vaccinated female subjects will visit the study site for every study visit. If not possible, the child may be visited at home by study site staff or a qualified health care worker for data collection.

Data collection can start when a signed informed consent form (ICF) is available for the current study. Preferably, signing of the ICF occurs at the last visit of the subject's original study (or at birth for offspring). If this is not possible, baseline data will be collected when a signed ICF is available and data need to be captured retrospectively up to the moment of enrollment in the current study.

Data collection will be as follows for the 3 cohorts:

Cohort 1: Data for subjects vaccinated with Ad26.ZEBOV and/or MVA-BN-Filo (or placebo) in a Phase 1, 2 or 3 clinical study (adults, adolescents and children) and who consent to participation in the current study will be collected in 6-month intervals. Data collection will continue for a total of 60 months after prime vaccination (including the duration in the subject's original study).

Cohort 2: Data on the pregnancy outcome of female subjects who became pregnant with estimated conception within 28 days after vaccination with MVA-BN-Filo (or placebo) or within 3 months after vaccination with Ad26.ZEBOV (or placebo) in a Phase 1, 2 or 3 clinical study

and who consent to participation in the current study will be collected at notification of the pregnancy, and at the end of the pregnancy. These subjects will be followed in Cohort 2 up to the end of their pregnancy. Thereafter, female subjects will continue to be followed in Cohort 1 (to reach a total of 60 months follow-up after prime vaccination including the duration in the subject's original study); live-born children will be followed in Cohort 3.

Cohort 3: Data for children born to female subjects exposed to Ad26.ZEBOV and/or MVA-BN-Filo (or placebo) in a Phase 1, 2 or 3 clinical study who became pregnant with estimated conception within 28 days after vaccination with MVA-BN-Filo (or placebo) or within 3 months after vaccination with Ad26.ZEBOV (or placebo) and for whom consent for the current study is given will be collected in 6-month intervals and up to 60 months after birth.

Each local authority will determine which cohorts will be opened for enrollment in their region. It is not mandatory to open all cohorts for enrollment. As a result, a local authority may restrict enrollment to 1 or 2 cohorts, rather than allowing enrollment in all cohorts.

After unblinding of their original study, subjects from Cohort 1 and 2 who received placebo or offspring (Cohort 3) from female subjects who received placebo will be discontinued from further participation in this roll-over study.

The study is considered completed with the last data collection time point for the last subject participating in the study. Further details of study completion and termination procedures are presented in Section 17.9.

Relevant Independent Ethics Committee (IEC)/Institutional Review Board (IRB) and Health Authority approvals will be secured prior to initiating the study.

3.2. Study Design Rationale

The prospective design of the study was chosen to specifically meet the study objectives. Prospective data collection facilitates active pharmacovigilance via real-time identification and reporting of serious adverse events and facilitates collection of a sufficient quantity of defined variables to address the study objectives of characterizing serious adverse events and pregnancy outcomes. The study design was chosen to observe long-term safety outcomes following Phase 1, 2 and 3 clinical studies.

4. TREATMENT ALLOCATION AND BLINDING

This section is not applicable, since no vaccine will be administered in the current study and subjects are already unblinded in their original Phase 1, 2 or 3 clinical study.

Unblinding of the ongoing Phase 2 and 3 studies has been delayed. Therefore, under Amendment 1, subjects who received placebo in their original Phase 2 or 3 study will also be approached for enrollment into the VAC52150 roll-over study before unblinding of their original study.

5. SUBJECT POPULATION

The study will be open to subjects who participated in a Phase 1, 2 and 3 clinical study with Ad26.ZEBOV and/or MVA-BN-Filo and who received at least one dose of study vaccine (active vaccine or placebo). Up to approximately 3,000 subjects may potentially be enrolled in this study, based on the number of exposed subjects in the contributing Phase 1, 2 or 3 clinical studies.

The inclusion and exclusion criteria for enrolling subjects in this study are described in the following 2 subsections. If there is a question about the inclusion or exclusion criteria below, the investigator must consult with the appropriate sponsor representative and resolve any issues before enrolling a subject in the study. Waivers are not allowed.

For a discussion of the statistical considerations of subject selection, refer to Section 11.2.

5.1. Inclusion Criteria

Each potential subject must satisfy all of the following criteria to be enrolled in the current study:

- 1. Criteria modified per amendment 1
- 1.1 Criterion modified per amendment 2
- 1.2 Male or female who participated in a Phase 1, 2 or 3 clinical study with Ad26.ZEBOV and/or MVA-BN-Filo and has been exposed to Ad26.ZEBOV and/or MVA-BN-Filo (or placebo) (Cohort 1);

or

Female who participated in a Phase 1, 2 or 3 clinical study with Ad26.ZEBOV and/or MVA-BN-Filo and became pregnant with estimated conception within 28 days after vaccination with MVA-BN-Filo (or placebo) or within 3 months after vaccination with Ad26.ZEBOV (or placebo) (Cohort 2);

or

Child born to a female subject exposed to Ad26.ZEBOV and/or MVA-BN-Filo (or placebo) in a Phase 1, 2, or 3 clinical study who became pregnant with estimated conception within 28 days after vaccination with MVA-BN-Filo (or placebo) or within 3 months after vaccination with Ad26.ZEBOV (or placebo) (Cohort 3).

Note: Each local authority will determine which cohorts will be opened for enrollment in their region. It is not mandatory to open all cohorts for enrollment. As a result, a local authority may restrict enrollment to 1 or 2 cohorts, rather than allowing enrollment in all cohorts.

2. Must sign an ICF for the current study (or their legally acceptable representative must sign) indicating that he or she understands the purpose of, and procedures required for, the study and is willing to participate in the study (or let their child participate).

Note: Assent is also required of children capable of understanding the nature of the study (typically 7 years of age and older) as described in Section 16.2.3.

5.2. Exclusion Criteria

No exclusions beyond those not meeting the inclusion criteria will be made for participation.

6. DOSAGE AND ADMINISTRATION

This section is not applicable, since no vaccine will be administered in the current study. For details on the administered study vaccine, refer to the protocol of the subject's original study.

7. TREATMENT COMPLIANCE

This section is not applicable, since no study vaccine will be administered in the current study.

8. MEDICATION AND VACCINATIONS

After a signed ICF is obtained for the current study, medications taken for serious adverse events occurring within the entire study follow-up period of 60 months after prime vaccination (ie, limited to medication taken within a period of 30 days prior to the onset of a serious adverse event and up to the resolution of the serious adverse event), or vaccinations administered since exposure to Ad26.ZEBOV and/or MVA-BN-Filo (or placebo) (including routine vaccinations for children) will be documented from baseline (if not already present in the analysis data set from the subject's original study) until the end of data collection.

9. STUDY EVALUATIONS

9.1. Study Procedures

The Time and Events Schedule summarizes the frequency and timing of data collection in this study. The documentation of data must be performed according to Good Clinical Practice (GCP) and professional guidelines.

Prior to data collection, all subjects or their parent/legally acceptable representative (where applicable) must sign an ICF for the current study indicating that he or she understands the purpose of and procedures required for the study and is willing to participate in the study or let their child participate. Preferably, consent will be obtained at the last visit of the subject's original study or at birth for offspring. If this is not possible, the consent can be given at a later time point, allowing collection of baseline data to be conducted retrospectively up to the moment of enrollment in the current study. Relevant data should be copied from the analysis data set of the subject's original study. Any relevant new information should be added to the CRF of the current study.

Where available (and applicable to the cohort), the following items are to be documented or captured from the original analysis data set at baseline and/or during the long-term follow-up period:

- Demographic data (at baseline only);
- Serious adverse events
- Any medication taken within a period of 30 days prior to the onset of a serious adverse event and up to the resolution of serious adverse event;
- Vaccinations (including routine vaccinations for children);
- Pregnancy follow-up, including information on obstetric history, maternal/paternal risk factors, pregnancy outcome (including spontaneous/elective abortion, intrauterine death/stillbirth, information on delivery);
- Follow-up of offspring, including information on birth (preterm/full term), growth measurements at birth and subsequent visits (height and weight, including growth percentiles), presence of birth defects, medical interventions beyond routine interventions at birth. Medical history of the child may include relevant information from the mother's pregnancy follow-up, family history of growth (details on stature of parents and siblings).

Participating sites will enter data into the CRF into an electronic data collection (eDC) system. The CRF will direct the site regarding which data are required for collection. Participating sites will be trained on the use of the eDC system. Data collected should be recorded accurately, correctly and promptly for each subject during the study. Further details of CRF completion procedures are presented in Section 17.5.

The sponsor will perform on-site monitoring visits as frequently as necessary. The monitor will record dates of the visits in a site visit log that will be kept at the participating site. Further details of monitoring procedures are presented in Section 17.8.

When an enrolled subject completes or withdraws from the study, the investigator will complete an end-of-study form for the individual subject and provide a specific date for the end-of-study observation(s). When a subject withdraws before completing the study, the reason for withdrawal is to be documented in the CRF and in the source documents (see Section 10 for details).

After unblinding of their original study, subjects who received placebo will be withdrawn from further participation. This also applies to pregnant subjects who received placebo (ie, subjects enrolled in Cohort 2) or offspring from vaccinated female subjects who received placebo (ie, subjects enrolled in Cohort 3).

Subjects who appear to be lost to follow-up will be contacted, per local practice, and the data recorded in the CRF. Subjects unable to be reached within 365 days of their last follow-up will be considered "lost to follow-up" unless subsequent contact is established. Subjects lost to follow-up will have all data included for analysis unless the subject had specified upfront that their data is to be excluded from analysis.

9.2. Safety

9.2.1. Exposure Definition

Exposure to Ad26.ZEBOV and/or MVA-BN-Filo vaccines (or placebo) will be determined by documentation from the Phase 1, 2 and 3 clinical studies. The exposure date to any component of Ad26.ZEBOV and/or MVA-BN-Filo (or placebo) for each subject will be the vaccine administration date as obtained from the CRF from the subject's original study.

9.2.2. Evaluations

Serious Adverse Events

For the prospective study period, all serious adverse events, related or not related, following exposure of subjects to Ad26.ZEBOV and/or MVA-BN-Filo (or placebo) or in offspring are to be recorded in the CRF and in the subject's source documents.

Section 12 provides further details of safety reporting procedures.

Any serious adverse events persisting at the end of the study/early withdrawal will be followed by the investigator until resolution or until a clinically stable endpoint is reached.

Pregnancy Outcomes

For the prospective study period, all pregnancy outcomes (including spontaneous/elective abortion, intrauterine death/stillbirth, information on delivery) following pregnancy of a female subject who became pregnant with estimated conception within 28 days after vaccination with MVA-BN-Filo (or placebo) or within 3 months after vaccination with Ad26.ZEBOV (or placebo) are to be recorded in the CRF and in the subject's source documents.

Growth Measurements

For the prospective study period, growth measurements for offspring (including height, weight and growth percentiles) are to be recorded in the CRF and in the subject's source documents.

9.2.3. Endpoints

Refer to Section 11.1 for the endpoints.

10. SUBJECT COMPLETION/WITHDRAWAL FROM THE STUDY

When an enrolled subject completes or withdraws from the study, the investigator will complete an end-of-study form for the individual subject and provide a specific date for the end-of-study observation(s).

10.1. Completion

Cohort 1: Data for subjects vaccinated with Ad26.ZEBOV and/or MVA-BN-Filo (or placebo) in a Phase 1, 2 or 3 clinical study (adults, adolescents and children) and who consent to participation in the current study will be collected in 6-month intervals. Data collection will

continue for a total of 60 months after prime vaccination (including the duration in the subject's original study).

Cohort 2: Data on the pregnancy outcome of female subjects who became pregnant with estimated conception within 28 days after vaccination with MVA-BN-Filo (or placebo) or within 3 months after vaccination with Ad26.ZEBOV (or placebo) in a Phase 1, 2 or 3 clinical study and who consent to participation in the current study will be collected at notification of the pregnancy, and at the end of the pregnancy. These subjects will be followed in Cohort 2 up to the end of their pregnancy. Thereafter, female subjects will continue to be followed in Cohort 1 (to reach a total of 60 months follow-up after prime vaccination including the duration in the subject's original study); live-born children will be followed in Cohort 3.

Cohort 3: Data for children born to female subjects exposed to Ad26.ZEBOV and/or MVA-BN-Filo (or placebo) in a Phase 1, 2 or 3 clinical study who became pregnant with estimated conception within 28 days after vaccination with MVA-BN-Filo (or placebo) or within 3 months after vaccination with Ad26.ZEBOV (or placebo) and for whom consent for the current study is given will be collected in 6-month intervals, and up to 60 months after birth.

Refer to Section 10.2 for details on the withdrawal of subjects after unblinding of their original study.

10.2. Withdrawal From the Study

A subject may be withdrawn from data collection in this study for any of the following reasons:

- Withdrawal of consent
- Lost to follow-up
- Death

After unblinding of their original study, subjects who received placebo will be withdrawn from further participation. This also applies to pregnant subjects who received placebo (ie, subjects enrolled in Cohort 2) or offspring from vaccinated female subjects who received placebo (ie, subjects enrolled in Cohort 3).

Subjects who are subsequently enrolled as a subject in another non-sponsor clinical study do not need to be withdrawn from the study. It is accepted that data collection in this study may be restricted by confidentiality agreement terms and/or conditions of another concurrent clinical study.

When a subject withdraws before completing the study, the reason for withdrawal is to be documented in the CRF and in the source documents.

If a subject is lost to follow-up, every reasonable effort must be made by the study-site personnel to contact the subject and determine the reason for withdrawal. The measures taken to follow up must be documented. In the event that the status of the subject cannot be determined and the

subject is considered to be lost to follow-up, an end-of-study form for the individual subject will be completed and a specific date for the last observation will be provided.

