2. COHORT 2: PREGNANCY OUTCOMES

Data collection schedule for female subjects who became pregnant with estimated conception within 28 days after vaccination with MVA-BN-Filo (or placebo) or within 3 months after vaccination with Ad26.ZEBOV (or placebo) in a Phase 1, 2, or 3 clinical study:

	Visit 1 ^a	End of Pregnancy Follow-up ^a	
	Baseline (Start of Data Collection) ^b	End of Pregnancy	
Subject information			
Subject consent ^c	X		
Selection criteria	X		
Demographics ^d	X		
Ongoing subject review			
Serious adverse events ^{d,e}	X	X	
Medication and vaccinations ^{d,f}	X	X	
Pregnancy follow-upg	X	X	
Study completion/withdrawal			
Transition to Cohort 1h		X¹	

- a. Only the first visit is a study site visit; data collection at the end of the pregnancy will preferably occur through a phone call. If not possible by phone, a study site visit needs to be organized.
- b. Data collection can start when a signed ICF is available for the current study. Preferably, this occurs at the last visit of the subject's original study. If this is not possible, baseline data will be collected when a signed ICF is available and data will be captured retrospectively from the subject's last visit in the original study up to the moment of enrollment in the current study.
- c. Before the start of data collection in this study, all subjects and/or their legally-acceptable representative (where applicable) must sign an ICF for the current study indicating that he or she understands the purpose of and procedures required for the study and is willing to participate in the study.
- d. Relevant data will be copied from the analysis data set of the subject's original study. Any relevant new information should be added in the CRF of the current study.
- e. All serious adverse events in subjects exposed to Ad26.ZEBOV (or placebo) and/or MVA-BN-Filo (or placebo) are to be documented. Data collection should start with study enrollment and continue until the end of the pregnancy.
- f. Any medication taken within a period of 30 days prior to the onset of a serious adverse event and up to the resolution of the serious adverse event.
- g. Information on obstetric history, maternal/paternal risk factors, pregnancy outcome (including spontaneous/elective abortion, intrauterine death/stillbirth, information on delivery).
- h. After the pregnancy, female subjects will continue to be followed up in Cohort 1. A live-born child will be followed up in Cohort 3.

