11.3. Analysis Sets

The Full Analysis set includes all subjects who were enrolled in this study and have at least one post-baseline visit, regardless of the occurrence of protocol violations.

The Restricted Analysis set includes all subjects who were enrolled in this study and have at least one post-baseline visit, have no major protocol deviations deemed to affect safety endpoints and have not been enrolled in any other clinical study.

The study endpoints will be analyzed based on the Full Analysis set as the primary analysis population. Additionally, the study endpoints may be analyzed based on the Restricted Analysis set as a secondary analysis population (sensitivity analysis).

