11.5. Safety Analyses

The verbatim terms used in the CRF by investigators to document serious adverse events will be coded using the Medical Dictionary for Regulatory Activities (MedDRA). All serious adverse events will be included in the analysis. For each serious adverse event, the percentage of subjects who experience at least 1 occurrence of the given event and the number of events per person-year (where applicable) with corresponding 2-sided 95% confidence intervals will be provided, for each cohort and by original randomization (active vaccine versus placebo). In addition, these analyses will be provided by age group for Cohort 1.

The incidence of pregnancy, incidence of pregnancy outcomes (including spontaneous/elective abortion, intrauterine death/stillbirth, information on delivery) and incidence of live-born children will be summarized by original randomization (active vaccine versus placebo). Only pregnancies with estimated conception within 28 days after vaccination with MVA-BN-Filo or within 3 months after vaccination with Ad26.ZEBOV, and live-born children from these pregnancies, will be included.

Results for subjects who received active vaccine or placebo will be presented separately.

A summary for subjects who die or who discontinue due to a serious adverse event will be provided.

The use of medications taken in relation to serious adverse events will be summarized.

Additional summaries, listings, datasets, or subject narratives may be provided, as appropriate.

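### Placebo women still pregnant at unblinding leave before their outcome is collected, so the placebo column of the pregnancy tables keeps early losses and drops deliveries

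*Protocol*

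**What the plan says.** The withdrawal rule is in Protocol Section 10.2: "After unblinding of their original study, subjects who received placebo will be withdrawn from further participation". The next sentence extends it: "This also applies to pregnant subjects who received placebo (ie, subjects enrolled in Cohort 2", and also to offspring of placebo recipients in Cohort 3. The Synopsis and Sections 3.1 and 9.1 carry the same rule. None of them allows a pregnancy to finish first.

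The rule acts on one arm. Section 3.1: "After unblinding of their original study only subjects who received Ad26.ZEBOV and/or MVA-BN-Filo will remain in this" study. For everyone else in Cohort 2, Section 10.1 applies: "These subjects will be followed in Cohort 2 up to the end of their pregnancy". Section 10.1 closes by referring to Section 10.2 for withdrawals after unblinding.

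The Time and Events Schedule for Cohort 2 has a baseline visit and one later column: "data collection at the end of the pregnancy will preferably occur through a phone call". Section 9.2.2 asks for outcomes to be recorded, placebo included, with the opening "For the prospective study period, all pregnancy outcomes". Section 12.3.2 says that pregnancy outcome data are collected in this study.

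On analysis, the Full Analysis set in Section 11.3 is primary; this "set includes all subjects who were enrolled in this study and have at least one post-baseline visit, regardless of the occurrence of protocol violations". Section 11.5 covers pregnancies, their outcomes and live births; the last part reads "incidence of live-born children will be summarized by original randomization (active vaccine versus placebo". Section 11.1 does not name a denominator for the incidence of pregnancy by outcome.

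**The concern.** Unblinding is a study-level event and is not triggered by any woman's outcome. It still selects on outcome, because a pregnancy that lasts longer is more likely to be ongoing when unblinding occurs. A pregnancy lost early has usually been recorded by then; one heading for delivery may not have been. With no contact between baseline and the end of pregnancy, the interrupted pregnancy leaves no outcome, and no later analysis can recover it.

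Because only placebo women are cut off, the distortion falls in one column of a table laid out by arm. At stake is whether the placebo figures can serve as background for the vaccine figures. If placebo losses look too frequent, an excess on vaccine is harder to see.

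**Working it through.** The protocol gives no pregnancy count, loss rate or power figure, so there is nothing of its own to reproduce. The calculation shows direction and possible size under stated assumptions.

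**Inputs from the protocol.** Placebo only is cut off (3.1, 9.1, 10.2). One post-baseline data point in Cohort 2 (Time and Events Schedule). Summary by arm (11.5). Primary set requires a post-baseline visit (11.3).

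**Assumptions, not in the protocol.** True loss proportion 15%; all losses occur early and are recorded; a fraction c of the pregnancies still ongoing, all of which would end in live birth, is cut off at unblinding. Values of c are illustrative.

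**Step 1: which denominator.** The only scheduled post-baseline contact in Cohort 2 is the end of pregnancy. A woman withdrawn before it would normally fall outside the Full Analysis set, unless a withdrawal contact or a Cohort 1 contact counts as a post-baseline visit. The primary set therefore points to known outcomes as the denominator.

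**Step 2: known outcomes.** Per 100 placebo pregnancies, loss share = 15 / (15 + 85(1 − c)):
- c = 10%: 15/91.5 = 16.4%
- c = 30%: 15/74.5 = 20.1%
- c = 50%: 15/57.5 = 26.1%

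If vaccine truly raised losses by a ratio of 1.5, to 22.5%, the table would show 22.5/16.4 = 1.37, 22.5/20.1 = 1.12 and 22.5/26.1 = 0.86.

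**Step 3: all enrolled pregnancies.** The loss share stays 15/100 = 15%. Live births per pregnancy = 85(1 − c)/100 = 76.5%, 59.5% and 42.5%, against a true 85%.

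**Step 4: small numbers.** Take 20 placebo pregnancies with 3 early losses and 17 eventual live births. If 0, 2, 5 or 10 women are withdrawn while pregnant, the loss share among known outcomes is 3/20 = 15.0%, 3/18 = 16.7%, 3/15 = 20.0% or 3/10 = 30.0%, and recorded live births are 17, 15, 12 or 7.

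**Step 5: relaxing the assumption that every loss is early.** A simulation put 85% of losses before week 20 and live births at weeks 37 to 41. For a share f of placebo pregnancies, unblinding fell uniformly within weeks 5 to 41. At a true loss risk of 15%:

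| f | Placebo loss share, known outcomes | True loss ratio 1.5 appears as | Placebo live births per enrolled pregnancy |
|---|---|---|---|
| 0.10 | 15.9% | 1.41 | 77% |
| 0.25 | 17.7% | 1.27 | 65% |
| 0.50 | 22.3% | 1.01 | 45% |
| 0.75 | 32.2% | 0.70 | 25% |

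At f = 0.50, a true 1.5 appears as 0.98 with a 10% loss risk and 1.07 with 25%, so the direction does not hinge on the 15%. With all enrolled pregnancies as denominator and 15% risk, some placebo losses are also missed, and a true loss ratio of 1.5 appears as 1.54 to 1.91 over the same values of f.

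**Step 6: when can it happen.** The longer conception window is 3 months (Ad26.ZEBOV). Adding an assumed 9-month gestation, a pregnancy can be caught only if unblinding falls within about 12 months of the relevant dose.

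**The case against.** A reader might set Section 10.1, with its follow-up to the end of pregnancy, against Section 10.2 and call it a contradiction. The text does not support that: 10.1 refers to 10.2 for this case, the rule is worded consistently wherever it appears, and the recording duty in 9.2.2 is limited to the prospective study period. The cut-off is deliberate.

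A reader might also infer that the loss and live-birth errors both make the vaccine look safer. That mixes two denominators. Inflated losses need known outcomes; depressed live-birth incidence needs all enrolled pregnancies. With all pregnancies throughout, the placebo loss share is not inflated, and the vaccine may even look slightly worse on losses.

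The strongest defence is that placebo is not a planned comparator. Objectives and endpoints concern vaccine exposure, placebo recipients came in only because unblinding was delayed, Section 11.7 calls the study non-comparative, and Section 11.6 plans no formal test. It is also true that vaccinated women can be lost to follow-up, as Section 11.2 acknowledges, and that few or no placebo women may be pregnant at unblinding. All of this limits the harm. It does not make the placebo column correct: Section 11.5 requires outcomes by randomized arm, and readers will compare them.

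Leaving the matter to the statistical analysis plan, which is not at hand, helps only in part. Handling by gestational age could reduce the bias of a crude proportion, but the deliveries themselves would remain uncollected.

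**Conclusion.** The point holds as a minor one. The protocol sets a deliberate, one-sided cut-off that removes mainly deliveries from placebo pregnancy data, and then tabulates those data by arm. Under the known-outcome denominator to which the Full Analysis set points, the placebo loss share is too high and a vaccine effect on losses can be masked. Under an all-pregnancies denominator, the error moves to live births.

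The percentages above illustrate sensitivity and are not expected values. The protocol gives no placebo pregnancy count, unblinding dates or original-study durations, so the number affected is unknown and may be zero. The consequence is a descriptive table that can mislead, not a wrong test. The direction rests on losses occurring earlier in gestation than deliveries and, for masking of losses, on withdrawn women being absent from the denominator.

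**What to change.** In the Synopsis and Sections 3.1, 9.1 and 10.2, let placebo women who are pregnant in Cohort 2 at unblinding stay until the end-of-pregnancy contact already scheduled, and then discontinue without moving to Cohort 1 and without their child entering Cohort 3. All of these places need the same wording, or the amended text will conflict with the rest.

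For outcomes that remain unknown in either arm, for example after withdrawal of consent, report a separate category of unknown or ongoing at exit, by gestational age at exit. Do not simply drop these pregnancies from the denominators: that is the known-outcome proportion of Step 2 and brings the same bias back.

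The cost is amendment wording and one contact, preferably by telephone, for each woman concerned. The downside is that a few placebo women stay in the study some months after unblinding.
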